The South African National TB Programme (NTP) does not recommend a course of isoniazid preventive therapy (IPT) for HIV-uninfected adults and children older than 5 years of age with asymptomatic (latent) *Mtb* infection, due to the high risk of reinfection after completion of IPT in this high TB prevalence region. Subjects in this trial will be managed according to current NTP guidelines. However, since QFT-GIT conversion is known to be associated with increased risk of active TB disease, symptom screening for early diagnosis and treatment of incident TB disease will be a safety priority, and all subjects who are found to be QFT-GIT positive (including at screening) will be educated on the symptoms of TB and the benefits of early diagnosis and treatment. Screening for symptoms compatible with incident TB disease, including unexplained cough, fever, night sweats, or loss of weight for longer than two weeks duration will continue throughout the study. Subjects with one or more compatible symptoms will be asked to provide two sputum samples for smear microscopy, mycobacterial culture, and GeneXpert. Subjects who are sputum smear negative or unproductive may also undergo chest radiography or additional investigations, including repeat HIV testing, as clinically indicated. Subjects with a microbiological, radiological, and/or clinical diagnosis of TB disease will be referred to the NTP for TB treatment (directly observed, short course), which is provided free of charge by the NTP. For the purposes of the exploratory TB disease objective, a bacteriologically confirmed case of active TB disease will be defined as clinical evidence of TB with positive *Mtb* MGIT culture, or GeneXpert MTB/RIF (Cepheid, USA), from sputum or an extra-pulmonary site. A clinical case

of active TB disease will be defined as clinical and/or radiographic evidence of active TB disease that is not bacteriologically confirmed (as defined above).

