- Clinical TB diagnosis and assessment.
- QuantiFERON positivity patterns over time.
- Participants who QFT-GIT converted, reverted and then converted again.

The following QuantiFERON variables, as presented in the planned TLF shells, will be collected on the QuantiFERON and QuantiFERON Re-valuation eCRFs:

- Date of sample collection.
- Qualitative results:
  - o Negative.
  - o Positive.
- Quantitative Result:
  - o QFT-Nil (IU/mL).
  - o QFT-Ag (IU/mL).
  - o QFT-Mitogen (IU/mL).

The following TB diagnosis variables, as presented in the planned TLF shells, will be collected on the TB Assessments – First Sputum Sample and TB Assessments – Second Sputum Sample eCRFs:

- Date of sputum sample collection.
- Sputum smear result:
  - o Acid- Fast Bacilli (AFB) seen:
    - Scanty.
    - 1+.
    - 2+.
    - 3+.
  - o No AFB seen.
  - o No result.
- Sputum culture result:
  - o Mycobacterium positive.
  - o Mycobacterium negative.

---

Document: Aeras\_C-040-404\_SAP\_V2\_0

Author: [name]

Version Number:

2.0

Version Date:

29SEP2017

Template No: CS\_TP\_BS016 – Revision 3

Reference: CS\_WI\_BS005

Effective Date: 01May2012

Copyright © 2012 Quintiles Transnational Corp. All rights reserved.

The contents of this document are confidential and proprietary to Quintiles Transnational Corp. Unauthorized use, disclosure or reproduction is strictly prohibited.

- o Contaminated.
  - o No result.
- Differential test for positive Culture:
  - o MTB.
  - o Mycobacterium other than tuberculosis (MOTT) (specify).
- GeneXpert result:
  - o Invalid.
  - o No result.
  - o MTB not detected.
  - o MTB detected.

The following TB diagnosis variables, as presented in the planned TLF shells, will be collected on the TB Clinical Evidence eCRF:

- TB clinical signs and symptoms:
  - o Unexplained cough for more than two weeks.
  - o Fever for more than two weeks.
  - o Night sweats for more than two weeks.
  - o Unexplained weight loss.
  - o Recent history of Hemoptysis.
  - o Other (specify).

The following TB diagnosis variables, as presented in the planned TLF shells, will be collected on the Chest X-Ray eCRF:

- Chest x-ray performed:
  - o Yes.
  - o No.
- Chest x-ray result:
  - o Normal.
  - o Abnormal.

The following clinical TB diagnosis variable, as presented in the planned TLF shells, will be collected on the TB Case Assessment eCRF:

- o Was a clinical case of TB diagnosed?

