    TABLE Events / BINOMIAL (midp P=0.05);
RUN;
```

Based on the exact 95% CI for  $\pi$ , an exact 95% CI ( $\theta_L, \theta_U$ ), for the rate ratio  $\theta$  is then calculated by solving the equations:

$$\frac{\theta_L F_A}{\theta_L F_A + F_B} = \pi_L$$

$$\frac{\theta_U F_A}{\theta_U F_A + F_B} = \pi_U$$

Solving  $\theta_L$  and  $\theta_U$  yields:

$$\theta_L = \left( \frac{\pi_L}{1 - \pi_L} \right) \left( \frac{F_B}{F_A} \right)$$

$$\theta_U = \left( \frac{\pi_U}{1 - \pi_U} \right) \left( \frac{F_B}{F_A} \right)$$

Finally, the exact 95% CI ( $VE_L, VE_U$ ) for VE is calculated as

$$VE_L = (1 - \theta_U)$$

$$VE_U = (1 - \theta_L)$$

In summary, the VE point estimate and confidence limits for the aforementioned binomial proportion ( $\pi$ ) will be substituted in the following formula in order to obtain the corresponding confidence limits for the VE:

$$VE = \left( \frac{(\pi) F_B}{(1 - \pi) F_A} \right)$$

Document: Aeras\_C-040-404\_SAP\_V2\_0

Author: [name]

Version Number:

2.0

Version Date:

29SEP2017

Template No: CS\_TP\_BS016 – Revision 3

Reference: CS\_WI\_BS005

Effective Date: 01May2012

Copyright © 2012 Quintiles Transnational Corp. All rights reserved.

The contents of this document are confidential and proprietary to Quintiles Transnational Corp. Unauthorized use, disclosure or reproduction is strictly prohibited.

Where the lower confidence limit for VE is obtained by substituting the upper confidence limit for  $\pi$  in the above formulae, and the upper confidence limit for VE is obtained by substituting the lower confidence limit for  $\pi$  in the above formula.

- Bacteriologically confirmed TB:
  - o Positive culture result (Mycobacterium tuberculosis positive)  
OR
  - o Positive GeneXpert result (MTB detected) (with or without clinical symptoms and/or positive chest x-ray).

---

Document: Aeras\_C-040-404\_SAP\_V2\_0

Author: [name]

Version Number:

2.0

Version Date:

29SEP2017

Template No: CS\_TP\_BS016 – Revision 3

Reference: CS\_WI\_BS005

Effective Date: 01May2012

Copyright © 2012 Quintiles Transnational Corp. All rights reserved.

The contents of this document are confidential and proprietary to Quintiles Transnational Corp. Unauthorized use, disclosure or reproduction is strictly prohibited.

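### The SAP derives bacteriologically confirmed and clinical TB by a looser rule than Protocol 3.6.1: no clinical evidence needed, no listed source for extra-pulmonary results, and no bar on one case filling both rows

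*SAP*

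**What the plan says.** Protocol 3.6.1 sets two case definitions for the exploratory TB disease objective. In the first, "a bacteriologically confirmed case of active TB disease will be defined as clinical evidence of TB with positive" culture or GeneXpert, and the specimen may come "from sputum or an extra-pulmonary site". The second, a clinical case, is "clinical and/or radiographic evidence of active TB disease that is not bacteriologically confirmed (as defined above"). The two protocol categories therefore cannot overlap.

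SAP 14.3.3 derives bacteriologically confirmed TB from either of two results: "Positive culture result (Mycobacterium tuberculosis positive"), or "Positive GeneXpert result (MTB detected) (with or without clinical symptoms and/or positive chest x-ray"). Neither line names a specimen. According to SAP 14.3.2, the smear, culture and GeneXpert variables "will be collected on the TB Assessments – First Sputum Sample and TB Assessments – Second Sputum Sample eCRFs".

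The clinical TB diagnosis table in SAP 14.3.2 shows confirmed TB and clinical TB as separate categories among participants who had a work-up. It is planned for the modified intent-to-treat set and repeated for the per-protocol set. The clinical category rests on the investigator's assessment. The case-assessment item listed for it is "Was a clinical case of TB diagnosed", and no exclusion of confirmed cases is stated.

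**The concern.** The two documents use the same category names for different sets of participants. Anyone reading the TB table against the protocol would assume that a confirmed case had clinical evidence of disease, that extra-pulmonary disease was included, and that the two rows add up to the number of TB cases in each arm. The SAP as written guarantees none of these.

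TB cases are few, and Protocol 2.2 says they are captured as part of the safety assessment. With so few, one participant placed in a different row, or in two rows, is a visible share of the total.

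**Working it through.** **Side-by-side classification.** Applying each document's wording to four kinds of participant gives:

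| Participant | Protocol 3.6.1 | SAP 14.3.2 and 14.3.3 |
|---|---|---|
| Clinical evidence and a positive sputum test | Confirmed only | Confirmed; also clinical if the investigator answers yes |
| Positive sputum test, no clinical or radiographic evidence | Neither | Confirmed |
| Clinical evidence, positive test from an extra-pulmonary site only | Confirmed | No listed route to confirmed; clinical if the investigator answers yes |
| Clinical or radiographic evidence, no positive test | Clinical | Clinical if the investigator answers yes |

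Only the last row is sure to agree, given a yes from the investigator. The second row is an explicit difference: the SAP waives clinical evidence in words for GeneXpert and attaches no clinical condition to culture. The first and third rows differ because the SAP is silent on exclusivity and on specimen.

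**Scale.** The inputs are 990 participants randomized 1:1:1 (Protocol 2.2) and an expected TB incidence of 0.2% a year, stated there as about 2 cases per year.

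- Reproducing the protocol's figure: 990 × 0.002 = 1.98 cases per year, which agrees with 2.
- Expected total = 1.98 × years of follow-up; expected per arm = total / 3; chance of no case in a given arm = exp(−expected per arm), treating cases as Poisson.

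| Follow-up | Total | Per arm | Chance of no case in an arm |
|---|---|---|---|
| 15 months | 1.98 × 1.25 = 2.48 | 0.83 | 44% |
| 21 months | 1.98 × 1.75 = 3.46 | 1.16 | 32% |
| 24 months | 1.98 × 2 = 3.96 | 1.32 | 27% |

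With 2 to 4 cases in all, one case classified differently is 1/2 = 50% to 1/4 = 25% of the total. These totals assume that all 990 participants are followed for the whole period. The table uses smaller sets (the modified intent-to-treat set requires a negative Day 84 result), so the expected counts there are somewhat lower.

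The number of participants who would change category cannot be computed. The documents give neither the number of work-ups nor the frequency of positive tests without clinical evidence.

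**The case against.** The strongest reply is that the difference may hardly affect any case.

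- **Clinical evidence.** Protocol 3.6.1 asks for sputum from participants with compatible symptoms, and the SAP's TB clinical evidence form records those symptoms. A positive result from a work-up of that kind would normally count as confirmed under either rule. This stands, and it is why the one explicit difference probably moves few cases or none.
- **Extra-pulmonary results.** SAP 14.3.3 excludes no specimen in words. This also stands: the gap is that no source is listed, not that such cases are ruled out.
- **Overlap.** An investigator who applies the protocol's meaning of a clinical case would answer no for a confirmed one. The table shells, which are not part of these documents, might add a hierarchy. That is possible, but the SAP text does not say so, and the form's question does not carry the protocol's exclusion.
- **Use of the table.** SAP 3.3 lists the exploration of TB incidence trends among analyses not done under this SAP, and Protocol 2.2 says the study is not powered for TB disease. What remains is a descriptive table. SAP 14.3.2 also plans a participant-level listing of TB diagnosis and assessment for the randomized set. With a handful of cases, a reader could probably reclassify each one from it. This limits the harm, but it does not make the table follow the protocol's definitions.

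A reader might also infer that the change was made without being declared. That cannot be established: the text between the visible end of SAP 3.3 and Section 4 is missing from the copy reviewed.

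**Conclusion.** The SAP's derivation departs from the protocol's case definitions, explicitly on clinical evidence and by omission on specimen and exclusivity. The point is minor. It affects a descriptive exploratory and safety table with about 2 expected cases a year, and no primary or secondary analysis depends on it.

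Three stronger readings go beyond the documents.

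- A percentage inflation of the confirmed row would need a work-up rate and a rate of isolated positive tests, and neither is given.
- A doubled case count would need every confirmed case to be answered yes on the clinical item, contrary to the protocol's definition, and the two rows then to be added, although the SAP text lists no total of cases.
- A reversed ordering of arms presumes a comparison of TB rates between arms, which the SAP does not plan.

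The documents show that the rules differ. They do not show that any count differs. The conclusion rests on the SAP text as it stands and would narrow if the table shells impose exclusivity or name an extra-pulmonary source.

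**What to change.** In SAP 14.3.3:

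1. Reconcile the confirmed TB derivation with Protocol 3.6.1, or declare the change and give the reason. If the protocol's condition is kept, say which recorded items count as clinical evidence. The chest X-ray result is listed only as normal or abnormal, so an X-ray judged compatible with TB cannot be derived from that field alone.
2. Define the clinical TB row as investigator-diagnosed TB that is not bacteriologically confirmed, so that the rows are mutually exclusive.
3. Add a total row of TB cases by arm.
4. Bring extra-pulmonary culture and GeneXpert results into the confirmed category from a named source.

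The cost is a few lines of SAP wording, a small derivation change and one extra table row. No new data collection is needed unless extra-pulmonary results are not recorded in a structured field, in which case they may have to be taken from case narratives for the few participants concerned.

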## 15. IMMUNOGENICITY

### 15.1. PERIPHERAL BLOOD MONONUCLEAR CELLS (PBMC) INTRACELLULAR CYTOKINE STAINING (ICS)

The following tables are planned for presentation (based on the Safety analysis set, in the Safety and Immunogenicity Cohort):

- Percent antigen-specific T cell negative control-subtracted ANY cytokine response and change from Baseline.
  - o Only the derived ANY cytokine combination will be included in this table.
  - o This table will include descriptive statistics and 95% confidence interval (CI) for the median based on order statistics at each applicable visit as well as the change from Baseline per T cell and stimulation antigen (including a 'total' stimulation antigen for Ag85B and TB10.4 combined).
  - o This table will be repeated for the negative-control ANY cytokine combination.
- Percent antigen-specific T cell negative-control subtracted Positive (G,2) cytokine response and change from Baseline.
  - o Only the derived Positive (G,2) cytokine combination will be included in this table.
  - o This table will include descriptive statistics and 95% confidence interval (CI) for the median based on order statistics at each applicable visit as well as the change from Baseline per T cell and stimulation antigen (including a 'total' stimulation antigen).
  - o This table will be repeated for the negative control Positive (G,2) cytokine combination.
- Number (percentage) of responders based on the derived Positive (G,2) cytokine combination.
  - o This is to include the number and percentage of responders (Refer to Section 15.1.2: Responder Status) at each visit per T cell and stimulation antigen.
  - o Percentages are based on the number of participants in the Safety analysis set within each treatment group with data available to determine responder status.
  - o P-values are also to be included and are based on a Fisher's EXACT test comparing each of the treatment groups.
- Comparisons of median negative control-subtracted ANY cytokine response.
  - o Only the derived ANY cytokine combination will be included in this table.
  - o This table will include the number of participants who have a negative control-subtracted negative-set-to-zero value available as well as the median of these values.
  - o P-values based on the Wilcoxon-Mann Whitney test for pair-wise comparisons between treatment groups will be performed.
- Comparisons of median negative control-subtracted Positive (G,2) cytokine response.
  - o Only the derived Positive (G,2) cytokine combination will be included in this table.
  - o This table will include the number of participants who have a negative control-subtracted negative-set-to-zero value available as well as the median of these values.
  - o P-values based on the Wilcoxon-Mann Whitney test for pair-wise comparisons between treatment groups will be performed.

---

Document: Aeras\_C-040-404\_SAP\_V2\_0  
Author: [name]

Version Number: 2.0  
Version Date: 29SEP2017

Template No: CS\_TP\_BS016 – Revision 3  
Effective Date: 01May2012

Reference: CS\_WI\_BS005

The following figures are planned for presentation (based on the Modified Intent-to-treat analysis set):

- Antigen-specific negative control-subtracted ANY cytokine response:
  - o Dot plot of antigen-specific negative control-subtracted ANY cytokine response per study day.
  - o One figure will be prepared for each stimulation antigen, including the derived total (Ag85B and TB10.4) stimulation antigen response; the median response will be represented by a horizontal line per treatment group and study day.
  - o Separate plots will be created per T cell (CD4+/CD8+).
  - o This figure will be repeated for the negative control ANY cytokine combination.
  - o Different symbols will be used to differentiate between responders (closed circles), non-responders (cross) and missing responder status (triangle) as based on the derived Positive (G,2) cytokine combination responder status.
- Antigen-specific negative control-subtracted Positive (G,2) cytokine response:
  - o Dot plot of antigen-specific negative control-subtracted Positive (G,2) cytokine response per study day.
  - o One figure will be prepared for each stimulation antigen, including the derived total (Ag85B and TB10.4) stimulation antigen response; the median response will be represented by a horizontal line per treatment group and study day.
  - o Separate plots will be created per T cell (CD4+/CD8+).
  - o This figure will be repeated for the negative control Positive (G,2) cytokine combination.
  - o Different symbols will be used to differentiate between responders (closed circles), non-responders (cross) and missing responder status (triangle) as based on the derived Positive (G,2) cytokine combination responder status.
- Antigen-specific negative control-subtracted ANY cytokine median response:
  - o Line plot of antigen-specific negative control-subtracted ANY cytokine median response per study day. Bars will be included, representing the first and third quartile per study day.
  - o One figure will be prepared for each stimulation antigen, including the derived total (Ag85B and TB10.4) stimulation antigen response; the median response will be represented by a dot and connected with a horizontal line across study days per treatment group.
  - o Separate plots will be created per T cell (CD4+/CD8+).
  - o This figure will be repeated for the negative control ANY cytokine combination.
- Antigen-specific negative control-subtracted Positive (G,2) cytokine median response:
  - o Line plot of antigen-specific negative control-subtracted Positive (G,2) cytokine median response per study day. Bars will be included, representing the first and third quartile per study day.
  - o One figure will be prepared for each stimulation antigen, including the derived total (Ag85B and TB10.4) stimulation antigen response; the median response will be represented by a dot and connected with a horizontal line across study days per treatment group.
  - o Separate plots will be created per T cell (CD4+/CD8+).
  - o This figure will be repeated for the negative control Positive (G,2) cytokine combination.
- Total (Ag85B and TB10.4) negative control-subtracted ANY cytokine response:
  - o Stacked bar plot of each stimulation antigen's median negative control-subtracted ANY cytokine response per study day.
  - o Separate plots will be created per T cell (CD4+/CD8+).
- Total (Ag85B and TB10.4) negative control-subtracted Positive (G,2) cytokine response:

---

Document: Aeras\_C-040-404\_SAP\_V2\_0

Author: [name]

Version Number:

2.0

Version Date:

29SEP2017

Template No: CS\_TP\_BS016 – Revision 3

Reference: CS\_WI\_BS005

Effective Date: 01May2012

Copyright © 2012 Quintiles Transnational Corp. All rights reserved.

The contents of this document are confidential and proprietary to Quintiles Transnational Corp. Unauthorized use, disclosure or reproduction is strictly prohibited.

- o Stacked bar plot of each stimulation antigen's median negative control-subtracted Positive (G,2) cytokine response per study day.
- o Separate plots will be created per T cell (CD4+/CD8+).
- Antigen-specific negative control-subtracted polyfunctional profile plots:
  - o Separate plots will be created per cytokine combinations of interest:
    - CD4+: IFN-g, IL-2, TNF, CD154.
    - CD4+: IFN-g, IL-2, IL-17, IL-22.
    - CD8+: IFN-g, IL-2, TNF, CD107a.
  - o Dot plot of participants' negative control-subtracted cytokine response per single-gate on the left hand side. Dot plot of participants' negative control-subtracted ANY cytokine response on the right hand side. The median response will be represented by a horizontal line per treatment group and cytokine combination.
  - o These figures will be repeated for the negative control.

The following listings are planned for presentation (based on the Safety analysis set):

- Percent antigen-specific T cell negative control-subtracted cytokine response and change from Baseline:
  - o Only derived cytokine combinations will be included in this listing.
- Percent antigen-specific T cell negative control-subtracted ANY cytokine response and total (Ag85B and TB10.4) vaccine response:
  - o Only derived cytokine combinations will be included in this listing.
- ICS responder status based on the Positive (G,2) response:
  - o The responder status for each antigen will be displayed, including the overall status.

The following PBMC ICS variables, as presented in the planned TLF shells, will be contained in the data received from Aeras:

- Stimulation antigen:
  - o Ag85B.
  - o BCG.
  - o TB10.4.
  - o Negative control:
    - DMSO for Ag85B and TB10.4.
    - R10 for BCG.
- T cell:
  - o CD4+.
  - o CD8+.
- Cell counts and percentages (including a total cell count) for each possible combination (alone and in combination with all other cytokines) of the following cytokines per stimulation antigen, study day and participant:
  - o IFN- $\gamma$  (+/-).
  - o TNF (+/-).
  - o IL-2 (+/-).
  - o IL-17A (+/-).
  - o IL-22 (+/-).
  - o CD154 (+/-).
  - o CD107a (+/-).

Document: Aeras\_C-040-404\_SAP\_V2\_0

Author: [name]

Version Number:

2.0

Version Date:

29SEP2017

Template No: CS\_TP\_BS016 – Revision 3

Reference: CS\_WI\_BS005

Effective Date: 01May2012

Copyright © 2012 Quintiles Transnational Corp. All rights reserved.

The contents of this document are confidential and proprietary to Quintiles Transnational Corp. Unauthorized use, disclosure or reproduction is strictly prohibited.

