### 3. STUDY DESIGN

#### 3.1. GENERAL DESCRIPTION

A Phase II, randomized, 3-arm, placebo-controlled, partially blinded clinical trial that was conducted in 990 healthy HIV-uninfected, QFT-GIT negative, previously BCG vaccinated adolescents. Participants were recruited from high schools or directly from the community.

Participants were enrolled in two sequential cohorts:

- Safety and Immunogenicity Cohort:
  - o First 90 participants (30 from each arm).
  - o More intensive collection of safety data.
  - o Selected immunogenicity assays (including whole blood intracellular cytokine staining [ICS]).
  - o Data reviewed by the data monitoring committee (DMC), principal investigator and local medical monitor.
- Correlates Cohort:
  - o Remaining 900 participants.

All 990 participants in the study were evaluated for:

- Safety outcomes.
- Biomarker outcomes.
- Prevention of *Mtb* infection.

Within each cohort, participants were randomized in a 1:1:1 ratio to one of the following treatment groups:

- H4:IC31:
  - o 15 mcg H4/500 nmol IC31.
  - o Two doses (administered on Day 0 and Day 56).
  - o Intramuscular injection.
- Placebo:
  - o Saline volume equivalent to the H4:IC31 injection.
  - o Two doses (administered on Day 0 and Day 56).
  - o Intramuscular injection.

---

Document: Aeras\_C-040-404\_SAP\_V2\_0

Author: [name]

Version Number:

2.0

Version Date:

29SEP2017

Template No: CS\_TP\_BS016 – Revision 3

Reference: CS\_WI\_BS005

Effective Date: 01May2012

Copyright © 2012 Quintiles Transnational Corp. All rights reserved.

The contents of this document are confidential and proprietary to Quintiles Transnational Corp. Unauthorized use, disclosure or reproduction is strictly prohibited.

- BCG:
  - o 2-8 x 10^5 CFU.
  - o One dose (administered on Day 0).
  - o Intradermal injection.

Randomization to the H4:IC31 and Placebo treatment groups was double-blinded. Since BCG causes a recognizable local injection site reaction, the BCG revaccination treatment group was not blind. Laboratory staff performing QFT-GIT, immunogenicity and correlates assays were blinded to all three treatment groups. Planned randomization of participants is specified in Table 1: Planned Enrollment by Treatment Group and Cohort, below:

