## 7. STATISTICAL CONSIDERATIONS

### 7.1. ADJUSTMENTS FOR COVARIATES AND FACTORS TO BE INCLUDED IN ANALYSES

Not applicable.

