Version Date: 29SEP2017

Template No: CS\_TP\_BS016 – Revision 3  
Effective Date: 01May2012

Reference: CS\_WI\_BS005

- Determine the responder status post-Baseline when taking Baseline (Day 0) into account:

Baseline (Determined in Step 1)	Day 70 (Determined in Step 2)	Responder Status
Non-responder	Non-responder	Non-responder
Non-responder	Responder	Responder
Responder	Non-responder	Non-responder
Responder	Responder	Determine responder status by means of the odds ratio

- Determine the odds ratio for results at Baseline. If the negative control positive count is zero, the odds ratio will be undefined. In these cases the positive negative control count should be imputed to 1 in order to determine an odds ratio.
- Determine the odds ratio for results at Day 70. If the negative control count is zero, the odds ratio will be undefined. In these cases the positive negative control count should be imputed to 1 in order to determine an odds ratio.
- Perform the Breslow-Day test:
  - Test for homogeneity of odds ratio at Day 70 and Baseline (Day 0).
  - P-value  $\geq 0.05$  indicates that the odds ratio at Baseline (Day 0) and Day 70 do not differ statistically significantly.
    - Participant classified as a non-responder at the relevant post-Baseline visit.
  - P-value  $< 0.05$  indicates that the odds ratio at Baseline (Day 0) and Day 70 visit differ statistically significantly.
    - Difference in log odds ratio should be evaluated in order to determine the responder status at Day 70.
- Calculate the difference in the log of the odds ratios at Day 70 and Baseline (Day 0).
  - Difference in log odds ratio =  $\log(\text{odds ratio at Day 70}) - \log(\text{odds ratio at Baseline [Day 0]})$ .
- Determine the responder status based on the Breslow-Day and difference in log odds ratio for cases where the Baseline (Day 0) and Day 70 visit was determined as responders:

Breslow-Day test p-value	Difference in log odds ratio	Responder status
$\geq 0.05$	$< 0$	Non-responder
$\geq 0.05$	$> 0$	Non-responder
$< 0.05$	$< 0$	Non-responder
$< 0.05$	$> 0$	Responder

The aforementioned steps will be implemented to determine the data record-level response per participant, T cell type, stimulation antigen (excluding negative control) and visit. In order to determine the response per participant at a day-level and therefore across T cell type and stimulation antigen, the following conventions will be used:

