## 15.2. WHOLE BLOOD ICS

The following tables are planned for presentation (based on the Safety analysis set, in the Safety and Immunogenicity Cohort). Aeras will be responsible for performing this analysis.

- Percent antigen-specific T cell negative control-subtracted cytokine response and change from Baseline.
- Number (percentage) of responders.
- Comparisons of median negative control-subtracted cytokine response.

These tables will be provided for the following cytokine combinations (including repeat tables for the negative control for each cytokine combination):

- CD4 cells producing Positive (G,2,T,17,22) cytokine combination.
- CD4 cells producing Positive (G,2,T) cytokine combination.
- CD8 cells producing Positive (G,2,T,17,22) cytokine combination.
- CD8 cells producing Positive (G,2,T) cytokine combination.
- CD4 cells producing Positive (17) cytokine combination.
- CD4 cells producing Positive (22) cytokine combination.

The following listings are planned for presentation (based on the Safety analysis set):

- Percent antigen-specific T cell negative control-subtracted cytokine response and change from Baseline:
  - o Only derived cytokine combinations will be included in this listing.
- Percent antigen-specific T cell negative control-subtracted cytokine response and total (Ag85B and TB10.4) vaccine response:
  - o Only derived cytokine combinations will be included in this listing.
- ICS responder status based on each derived cytokine response:
  - o The responder status for each antigen will be displayed, including the overall status.

---

Document: Aeras\_C-040-404\_SAP\_V2\_0

Author: [name]

Version Number:

2.0

Version Date:

29SEP2017

Template No: CS\_TP\_BS016 – Revision 3

Reference: CS\_WI\_BS005

Effective Date: 01May2012

Copyright © 2012 Quintiles Transnational Corp. All rights reserved.

The contents of this document are confidential and proprietary to Quintiles Transnational Corp. Unauthorized use, disclosure or reproduction is strictly prohibited.

The following whole blood ICS variables, as presented in the planned TLF shells, will be contained in the data:

- Stimulation antigen:
  - o Ag85B.
  - o BCG.
  - o TB10.4.
  - o Negative control:
    - UNS.
- T cell:
  - o CD4+.
  - o CD8+.
- Cell counts and percentages (including a total cell count) of the following cytokines per stimulation antigen, study day and participant:
  - o IFN- $\gamma$  and/or TNF and/or IL-2.

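### The between-arm tests of PBMC ICS response magnitude leave out the Day 0 value measured in the same participants, giving up precision with about 30 per arm

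*SAP*

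**What the plan says.** SAP Section 15.1 plans two tables that compare the size of the PBMC ICS response between arms, one for ANY and one for Positive (G,2). On the compared variable it says: "This table will include the number of participants who have a negative control-subtracted negative-set-to-zero value available as well as the median of these values". On the test it says: "P-values based on the Wilcoxon-Mann Whitney test for pair-wise comparisons between treatment groups will be performed". Neither table names a visit or a Day 0 term. SAP Section 7.1, on covariates, reads in full "Not applicable".

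Day 0 is used in two other places. The descriptive tables in Section 15.1 give each visit "as well as the change from Baseline per T cell and stimulation antigen", with a confidence interval for the median but no between-arm test. Section 15.1.2 sets out how to "Determine the responder status post-Baseline when taking Baseline (Day 0) into account", using a decision table, a Breslow-Day test and a difference in log odds ratios. Responder proportions are then compared between arms by Fisher's exact test. For PBMC that status is defined on Positive (G,2) only.

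For whole blood, SAP Section 15.2 lists "Comparisons of median negative control-subtracted cytokine response" without naming a test and assigns the work to the sponsor. Section 15.2.2 carries over only the responder method.

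Protocol Table 3-3 has ICS sampled at Day 0 and Day 70 in the Safety & Immunogenicity Cohort, 30 per arm. Immunogenicity is a secondary objective in both documents.

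**The concern.** Every participant had BCG at least five years earlier (protocol Section 3.2.3, criterion 6), and BCG is one of the stimulation antigens. It is plausible that people enter with responses that differ from one another and carry through to Day 70. The SAP itself allows for this in the responder algorithm, but not in the tests of magnitude.

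When the Day 0 value predicts the Day 70 value, a test that omits it counts between-person variation as noise. With about 30 per arm there is little to spare. A chance Day 0 difference between arms also adds to the imprecision of the comparison. For ANY, no planned between-arm test takes Day 0 into account.

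**Working it through.** **The only figure the documents attach to 30 per arm.** Protocol Section 7.6 gives 90% probability of seeing at least one adverse event of 7% frequency. Check: 1 − 0.93^30 = 0.887, which agrees within about a point. No power, effect size, SD or correlation is stated for any immunogenicity comparison, so what follows rests on assumptions.

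**Approximate formulas.** Let n be the number per arm, d the difference in SD units at Day 70, and ρ the Day 0–Day 70 correlation. Two-sided power at 0.05 is about Φ(d·√(n/2)/s − 1.96), where:
- Day 70 alone, parametric: s = 1
- Day 70 alone, Wilcoxon: s = 1, with n replaced by n × 3/π (normal shift model)
- Day 0-adjusted: s = √(1 − ρ²)
- change from Baseline: s = √(2(1 − ρ))

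Take n = 30 and d = 0.723, the shift that gives 80% for the parametric Day 70 comparison: (1.96 + 0.84) × √(2/30).
- Wilcoxon: effective n = 28.6, so Φ(2.74 − 1.96) = 78%
- Adjusted, ρ = 0.3: Φ(2.80/0.954 − 1.96) = 84%
- Adjusted, ρ = 0.5: Φ(2.80/0.866 − 1.96) = 90%
- Adjusted, ρ = 0.7: Φ(2.80/0.714 − 1.96) = 97.5%
- Change, ρ = 0.3: Φ(2.80/1.183 − 1.96) = 66%
- Change, ρ = 0.5: Φ(2.80/1 − 1.96) = 80%

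The adjusted analysis is worth 30/(1 − ρ²) participants per arm: 33, 40 and 59 at ρ = 0.3, 0.5 and 0.7.

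**Simulation of the rank tests.** Assumed: 28 evaluable per arm, d = 0.6, two-sided 0.05, no Holm adjustment, 2,000 to 4,000 runs per cell.

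| ρ | Wilcoxon, Day 70 | Rank ANCOVA on Day 0 |
|---|---|---|
| 0 | about 56% | 0–2 points lower |
| 0.3 | about 56% | about 60% |
| 0.5 | about 56% | 66–68% |
| 0.7 | about 56% | 78–82% |

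Setting 30% of values to a common floor, to mimic negatives set to zero, gives 59%, 66% and 79% for rank ANCOVA at ρ = 0.3, 0.5 and 0.7. Type 1 error is about 5–6% or less throughout.

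**If vaccination weakens the correlation in one arm.** With ρ = 0.7 under placebo and 0.3 under vaccine, rank ANCOVA reaches about 67–68%. With ρ = 0 under vaccine it reaches about 59–62%. The Wilcoxon stays at 54–57%.

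**Testing change instead.** With 30 per arm and d = 0.74, the Wilcoxon on change gives 49%, 64%, 78% and 94% at ρ = 0, 0.3, 0.5 and 0.7. The Wilcoxon on Day 70 gives 77–78% at every ρ. Change is therefore worse below ρ = 0.5.

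**Chance imbalance.** With no vaccine effect, about 19% of simulated trials show a Day 0 mean difference of at least 0.35 SD. Within those trials the Wilcoxon rejects 10% (ρ = 0.5) to 15% (ρ = 0.7) of the time, and rank ANCOVA 4–5%. Over all trials both hold about 5%.

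**The case against.** The strongest reply is that nothing is invalid. Randomisation protects the Wilcoxon test, and chance Day 0 imbalance is already inside its type 1 error. This stands. A reader might infer that the magnitude comparisons are biased, and the documents do not support that.

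A reader might also infer that every immunogenicity arm comparison ignores Day 0. That is wrong: the Fisher comparison rests on a Day 0-corrected status, and change from Baseline is tabulated. What remains is that the responder status discards magnitude, that ANY has no Day 0-corrected between-arm test, and that change is not tested.

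It would also go too far to say that the SAP tests Day 70 values, or that whole blood uses an unadjusted Wilcoxon. No visit is named for the PBMC tables and no test for the whole-blood ones. SAP Section 8 refers output content to table shells that are not among the documents and may say more.

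On importance, protocol Section 7.4.1 plans ICS as a preliminary, descriptive assessment, Section 7.6 sizes the cohort for adverse events, and SAP Section 7.4 says no definitive claims are sought. No stated power is contradicted and the primary endpoint is untouched. If the true effect is large, little is lost: at an assumed 1.0 SD the Wilcoxon already has about 94% power, and at 1.2 SD about 99%. These points limit the weight of the concern. They do not give a reason to leave a measured Day 0 value unused once p-values are planned.

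Holm does not settle the matter either way. SAP Section 7.4 names it for immunology data, but Section 15.1.2 spells it out only for within-participant responder p-values. The powers above do not include it.

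**Conclusion.** The concern holds as a point about efficiency. The PBMC magnitude tests for ANY and Positive (G,2) omit an available Day 0 measurement, and the visit compared is not stated. At the assumed 28 per arm and 0.6 SD, adjustment adds about 4 points of power at a correlation of 0.3, 10–12 at 0.5 and 22–26 at 0.7. It adds less if vaccination loosens the correlation in one arm, and costs 0–2 points at zero correlation. The omission is clear from the text. The size of the gain is not, because effect size, evaluable number and correlation are all assumed. The finding concerns precision in a secondary analysis without a power target.

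**What to change.** In SAP Section 15.1, name Day 70 as the visit compared and make the between-arm test of ANY and Positive (G,2) magnitude a rank ANCOVA on Day 0: rank the Day 70 and Day 0 responses across the arms being compared, regress the Day 70 ranks on the Day 0 ranks, and compare the residuals between arms. Ranks suit values set to zero. Keep the Wilcoxon test as supportive. Amend SAP Section 7.1 to list Day 0 response as a covariate for this analysis. In Section 15.2, where no test is named, specify the same method for whole blood. Do not switch to testing change from Baseline, which loses power when the correlation is below 0.5.

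The cost is a few lines of code and a short SAP amendment before unblinding for the final analysis. No new samples are needed. Participants without a Day 0 sample leave the adjusted test but stay in the supportive one.
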